#### 4.1.1 Primary Study Endpoints

1. Decrease in pain by 2 points on 0-10 numeric rating scale with activity, measured in each leg

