### 8 Study Analysis

#### 8.1 Sample Size Determination

Using a one-way ANOVA and assuming independence of leg scores for each patient, we will have 80% power to detect an overall significant F-test (assuming a 2 (SD=1) point decrease in pain score from baseline to 6 months) with n=6 patients (e.g. 12 legs). Accounting for potential drop-out (15%) and, additionally, adjusting for non-parametric analyses, **n=10 patients (e.g 20 legs) will be sufficient** to provide preliminary effect sizes at each time point which will help inform power analyses for studies planned beyond this pilot study.

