#### 8.2 Statistical Methods

Basic descriptive statistics, means (SD) and medians (IQR) for continuous variables and frequencies (percentages) for categorical variables will be used to summarize patient outcomes. For the primary outcome, change in pain (from baseline on 0-10 numeric rating scale) will be assessed at each time point (2,4,6 months) using Friedman's ANOVA. Friedman's ANOVA is the non-parametric analog to one-way repeated measures ANOVA and is often

used for ordinal outcomes. If necessary and feasible, GEE models will be constructed to further assess changes in pain while accounting for intra-subject correlation. Secondary endpoints utilizing the UWRI will also be assessed in this manner. Change in strength outcomes at baseline and 2 months will be assessed using Wilcoxon signed rank tests or, if necessary, linear mixed effects models for repeated measures, to account for intra-subject correlation (left and right legs).

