### **8.3 Subject Population(s) for Analysis**

The subject population for analyses will include all patients who receive the Botox injection. We intend to minimize loss to follow-up; however, if patients drop out of the study, we will attempt to use statistical methods that allow for missing outcomes (e.g. GEE/Linear models for repeated data) so that all available data can be used for analysis.

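### Section 8.2 does not make the patient the unit of analysis; if the two legs are pooled as independent, false positives for pain are about 9–17% (9–20% if baseline is a fourth level)

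*Combined protocol and SAP*

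**What the plan says.** The primary endpoint in 4.1.1 is defined per leg: "Decrease in pain by 2 points on 0-10 numeric rating scale with activity, measured in each leg". Section 4.1.2 likewise has the secondary parameters evaluated in each leg. Section 8.1 counts 10 patients as 20 legs and derives the size "assuming independence of leg scores for each patient".

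Section 8.2 gives the lead pain analysis: "change in pain (from baseline on 0-10 numeric rating scale) will be assessed at each time point (2,4,6 months) using Friedman's ANOVA". It does not name the Friedman block. A model that allows for correlation within a patient comes second and is conditional: "If necessary and feasible, GEE models will be constructed to further assess changes in pain while accounting for intra-subject correlation". For strength: "Change in strength outcomes at baseline and 2 months will be assessed using Wilcoxon signed rank tests or, if necessary, linear mixed effects models". The purpose given for those models is "to account for intra-subject correlation (left and right legs", so the plan knows that two legs of one person are related.

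Section 8.3 adds another route to GEE or linear models, but its occasion is dropout: "we will attempt to use statistical methods that allow for missing outcomes". It does not say whether the cluster is the leg or the patient.

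**The concern.** Friedman's test assumes independent blocks, and the signed rank test assumes independent differences. Two legs injected in the same person on the same day, and rated by that person over the same months, may well change together. If each leg is a block, the tests count 20 pieces of evidence where there are fewer, and p-values come out too small.

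The plan names suitable kinds of model but leaves their use to a later judgement of need and feasibility, which can be made after the data are seen. It also leaves their structure open, and with 10 patients the structure decides whether they work.

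The stake is modest but real. The primary objective is efficacy, and the stated product is "to provide preliminary effect sizes at each time point which will help inform power analyses for studies planned beyond this pilot study". Precision that is overstated here would carry into those calculations if legs were again counted as independent.

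**Working it through.** **Inputs from the documents.** 10 patients and 20 legs; 2-point decrease with SD 1; 80% power with 6 patients (12 legs); 15% dropout (8.1). Pain at 2, 4 and 6 months relative to baseline; strength at baseline and 2 months (8.2).

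**Assumed, because the documents do not give them.** Alpha 0.05. Between-leg correlation rho of 0.3, 0.5 and 0.8, where rho refers to the two legs' deviations over time. All 10 patients bilateral, then 5 of 10.

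**The plan's own figure.** One-way ANOVA over four time points, with a linear decline 0, −2/3, −4/3, −2 and SD 1. The squared deviations of the means sum to 2.222, so the noncentrality is n × 2.222.
- n = 6 per time point: 13.33, df 3 and 20, power 80.2%.
- n = 12 per time point: 26.67, df 3 and 44, power 99.2%.

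The stated 80% is therefore reproduced with 6 units per time point, not with 12 independent legs.

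**False-positive rates with legs pooled.** For b blocks and k levels, Friedman's Q = 12/[bk(k+1)] × Σ(Rj − b(k+1)/2)², referred to chi-square with k−1 df. Null data were simulated with 10 patients, two legs each and correlation rho between legs at each time (40,000 trials per cell). The share of p-values below 0.05 was:

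| Analysis | rho 0.3 | rho 0.5 | rho 0.8 |
|---|---|---|---|
| Friedman, 20 legs, 3 levels | 9% | 12% | 17% |
| Friedman, 20 legs, 4 levels (with baseline) | 9% | 13% | 20% |
| Friedman, 4 levels, only 5 patients bilateral | 7% | 10% | 14% |
| Wilcoxon, 20 leg changes | 8% | 11% | 14% |
| Wilcoxon, only 5 patients bilateral | 7% | 9% | 11% |
| Friedman, 4 levels, patient means | 4–5% | 4–5% | 4–5% |
| Wilcoxon, patient means | 5% | 5% | 5% |

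Scores rounded to whole numbers on 0–10, with ties, give the same four-level result (10%, 13%, 20%).

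A hand check for Wilcoxon: pooling inflates the variance by about 1 + rho, so the rate is about 2 × P(Z > 1.96/√(1+rho)) = 8.6%, 11.0% and 14.4%, in line with the simulation.

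**When there is no inflation.** If the legs share only a constant patient level, the pooled Friedman rate is about 5%, because ranking within a leg removes that level. If left and right are tested separately, each four-level Friedman test is at 4–5%.

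**Information in 20 legs.** The effective number is 20/(1+rho) = 15.4, 13.3 and 11.1.

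**The optional models, four levels, 10 bilateral patients, complete data.**
- GEE clustered on patient, uncorrected 3-df robust Wald test. With K clusters the rate is P(F(3, K−3) > 7.815(K−3)/(3K)). For K = 10 the threshold is 7.815 × 7/30 = 1.82, which gives 23% at any rho. The same statistic with an F reference gives about 5%.
- Mixed model with a leg random intercept only: 11%, 16%, 24%.
- Mixed model with a patient random intercept only: about 12%, 19%, 30%.
- F test with patient-by-time as the error term: about 5%.

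A random intercept fails because the correlation that matters here is between the legs' movements over time, not their levels.

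**The case against.** The strongest reply is that pooling is never stated. Section 8.2 does not name the block, and Friedman's test with the patient as block would be sound. The reproduced 80% fits 6 units per time point, which is compatible with thinking in patients. The visit tables (Table 3 in 7.2, Table 4 in 7.4.2) list UWRI, force measurement and side effects but no per-leg pain rating; if pain is recorded once per person, the pain problem disappears. The wording in 4.1.2 can also be read as separate left and right analyses. All of this stands, and it is why the figures here are conditional. It does not remove the point: the per-leg endpoint, the leg count and the independence assumption make pooled legs a natural way to carry out 8.2.

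A reader might infer that the plan overlooks left/right correlation. It does not: the strength sentence names it and gives it as the purpose of the mixed models, which could be read as applying them whenever both legs contribute. What is missing is a rule that makes such an analysis the default, above all for pain.

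It is also fair that this is an uncontrolled pilot meant to yield preliminary effect sizes. That lowers the stakes of any p-value, but the plan still names tests and an efficacy objective.

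**Conclusion.** The point holds in conditional form. Section 8.2 leaves the unit of its lead tests open, the rest of the plan points to the leg, and the methods that would deal with the two legs are optional and unspecified. With legs pooled, alpha 0.05, all patients bilateral and rho 0.3–0.8, the false-positive rate is about 9–17% for pain on the three follow-up levels and about 8–14% for strength.

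Two stronger readings are not supported. One is a flat 20% error rate: that needs baseline as a fourth level, pooled legs, every patient bilateral and rho 0.8 together. The other is that the estimated effects are wrong: when both legs are treated, mean changes are not biased, and only p-values and any intervals would be too favourable.

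This should be fixed before analysis. It does not threaten the study.

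**What to change.** In 8.2, make the patient the unit by default. Average the treated legs within each patient before the Friedman and Wilcoxon tests, and report leg-level values descriptively. Remove the conditional wording as the route by which correlation is handled.

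If models are kept, in 8.2 or under the dropout provision in 8.3:
- cluster any GEE on the patient, with a stated small-sample correction;
- include a patient-by-time term in any mixed model for pain, since a patient or leg intercept alone is not enough.

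In 4.1.2, analyse items recorded once per person (by their wording frustration, perceived recovery, running duration, running speed and confidence) once per patient.

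The cost is wording, a different grouping in the code and less favourable p-values. No new data are needed, and N=10 need not change. Under the plan's inputs (SD 1, linear 2-point decline) with independent time points and rho from 0.3 to 1, the patient-mean Friedman test has about 90–98% power with 10 patients and 79–94% with 8.

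### GEE is named as the follow-up model for pain with at most 10 patients and no small-sample correction; at usual defaults its nominal 5% tests would reject a true null about 10% (one visit) and 23% (all visits) of the time

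*Combined protocol and SAP*

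**What the plan says.** Pain is the primary endpoint and is recorded per leg: "Decrease in pain by 2 points on 0-10 numeric rating scale with activity, measured in each leg" (section 4.1.1). Section 8.2 assigns change in pain at 2, 4 and 6 months to Friedman's ANOVA and then adds: "If necessary and feasible, GEE models will be constructed to further assess changes in pain while accounting for intra-subject correlation". The secondary endpoints taken from the running index (UWRI) follow the same approach. For strength, section 8.2 names Wilcoxon signed rank tests or linear mixed models.

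For patients who drop out, section 8.3 says "we will attempt to use statistical methods that allow for missing outcomes (e.g. GEE/Linear models for repeated data", so GEE and linear models are both given as examples.

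Section 8.1 fixes the size: "n=10 patients (e.g 20 legs) will be sufficient", with 15% drop-out allowed for. Neither 8.2 nor 8.3 states a working correlation, a type of robust variance, a small-sample correction, a reference distribution, degrees of freedom, the cluster level or a significance level.

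**The concern.** GEE inference rests on a robust (sandwich) covariance that is estimated from the variation between clusters. It is reliable when there are many clusters. Here the independent unit is the patient: at most 10, and 8 or 9 after the planned drop-out (10 x 0.85 = 8.5). Counting 20 legs does not help, because two legs of one patient are not independent.

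With so few clusters the uncorrected sandwich variance is too small on average, and the z or chi-square reference ignores how poorly it is estimated. P-values come out too small and confidence intervals too narrow. GEE is the only model that section 8.2 names for within-patient correlation in pain, and one of two named for missing visits. The problem would therefore appear in just the analyses meant to deal with those features. A team planning a later trial from these intervals would see more precision than 10 patients can give.

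**Working it through.** **Inputs.** 10 patients, 2 legs, 15% drop-out (8.1); pain per leg (4.1.1); baseline plus 2, 4 and 6 months, hence 3 contrasts against baseline (8.2). Assumed, because the plan is silent: a 5% two-sided level; patient as cluster; uncorrected sandwich; z or chi-square reference.

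**The plan's own figure.** Section 8.1 claims "80% power to detect an overall significant F-test" with 6 patients, "assuming a 2 (SD=1) point decrease in pain score from baseline to 6 months". Take four time points, a linear fall (0, 0.67, 1.33, 2), SD 1 and 6 independent units. The noncentrality is 6 x (1 + 1/9 + 1/9 + 1) = 13.33, the critical value of F(3,20) is 3.098, and power is 0.802. The 80% reproduces with 6 independent units; 12 would give 0.99. So the patient count is the relevant one.

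**One visit contrast, default GEE.** With complete data the GEE estimate is the mean of the N patient-level changes (legs averaged). The uncorrected sandwich variance is (N-1)/N times the usual S²/N. So |z| > 1.960 is the same event as |t| > 1.960 x √((N-1)/N) on N-1 df.
- N = 10: |t(9)| > 1.859, probability 9.6%
- N = 9: |t(8)| > 1.848, probability 10.2%
- N = 8: |t(7)| > 1.833, probability 10.9%

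**Joint test of three visits, default GEE.** The Wald statistic W equals T² x N/(N-1), with T² Hotelling's statistic, and F = T² x (N-3)/(3(N-1)) on (3, N-3) df. W > 7.815 then means:
- N = 10: T² > 7.033, F(3,7) > 1.823, probability 23.1%
- N = 9: F(3,6) > 1.737, probability 25.9%
- N = 8: F(3,5) > 1.628, probability 29.5%

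**Simulation checks with 10 patients.** Over several assumed correlations, independence or exchangeable working correlation, and rounded 0-10 scores, rates were 9.1-10.0% and 23-24%. With 15% drop-out the joint rate was 24-26%. A standard GEE routine (1,500 fits) gave 9.7% and 24.3%. Clustering on leg instead of patient gave 12.6% and 24.7%, so the cluster level also has to be stated.

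**Does a corrected covariance suffice?** With complete data the Mancl-DeRouen correction multiplies the sandwich by (10/9)².
- One contrast against t(9): |t| > 2.262 x √(10/9) = 2.385, probability 4.1% (simulation 3.6-4.4%).
- Joint test against F(3,9): W/3 > 3.863, so T² > 11.588 x 10/9 = 12.875 and F(3,7) > 12.875 x 7/27 = 3.338, probability 8.6% (simulation 8.4-9.5%).
- Joint test with the Hotelling-scaled F(3,7): exactly 5% for complete normal data; simulation 5.0-5.5%, and 6.3% with drop-out and exchangeable working correlation.

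So for the joint test the reference distribution must change too.

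**Does a mixed model suffice?** Assume variance shares of patient 0.5, leg 0.2, patient-by-visit 0.15 and residual 0.15. The true variance of a visit contrast is 2 x (0.15/10 + 0.15/20) = 0.045. A model with only patient and leg-within-patient effects pools 30 df with expected mean square 0.15 and 27 df with expected mean square 0.15 + 2 x 0.15 = 0.45. That gives (4.5 + 12.15)/57 = 0.292 and a reported variance of 2 x 0.292/20 = 0.0292, too small by a factor of 1.54. In 20,000 complete-data null trials that model rejected 11.3% (one contrast) and 16.3% (joint). Adding the patient-by-visit effect gave 4.9% and 4.9%.

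**The case against.** The strongest reply is that GEE is not the primary analysis. Section 8.2 gives that role to Friedman's ANOVA; GEE is conditional and supplementary, in an open-label pilot whose stated aim is preliminary effect sizes. This stands, and it limits the point.

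Four stronger readings are tempting, and the documents do not support them:
- **The primary test is inflated.** The figures above are for GEE and say nothing about Friedman's test.
- **The effect sizes will be wrong.** The sandwich covariance does not enter the mean change or the outcome SD. Only standard errors, intervals and p-values are affected.
- **Missing visits force the plan into GEE.** Section 8.3 offers linear models as well, and both are examples.
- **The plan commits to uncorrected GEE.** It names no correction, but it rules none out. Also, its explicit mention of left and right legs belongs to the strength analysis; for pain it speaks only of correlation within subjects.

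It is also fair to say that the 5% benchmark is not the plan's. What remains is that silence usually leads to software defaults, and with 10 clusters those give the rates shown. The undefined trigger for fitting GEE is a separate weakness that does not depend on these rates, though naming the model beforehand would also deal with it.

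**Conclusion.** The point holds for the follow-up analysis. If GEE is run at usual defaults, a nominal 5% test has a true level of about 9-10% for one visit contrast and about 23% for the joint visit test with 10 patients, or about 11% and 29% with 8. Equivalently, a nominal 95% interval for one contrast covers about 90% (100 - 9.6).

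The result rests on an assumed 5% level, on the patient as cluster, and on the analyst accepting the defaults where the plan is silent. It depends very little on the assumed correlations, because the cause is the number of patients. It is worth correcting before analysis, but it does not undermine the primary test or the pilot's estimates.

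**What to change.** In 8.2 and 8.3, state the significance level and name one follow-up model for pain and the UWRI endpoints before data are seen. Either of these will do:

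(a) A linear mixed model on pain at 0, 2, 4 and 6 months, with visit as a factor, random effects for patient, leg within patient and patient-by-visit, and Kenward-Roger degrees of freedom. It uses all available visits. The patient-by-visit term is essential. The rates of about 5% were checked with complete data only.

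(b) GEE with the patient as cluster, a small-sample-corrected covariance such as Mancl-DeRouen, a t reference on patient-based degrees of freedom for single contrasts, and a Hotelling-scaled F for the joint visit test (F(3,7) with 10 patients). The scaling must match the covariance: with 10 patients and complete data, multiply the Wald statistic by 7/30 if the covariance is uncorrected, or by 10/9 x 7/27 = 70/243 if it is Mancl-DeRouen. An F(3,9) reference is not enough.

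Friedman's ANOVA can stay as the primary test. The cost is a few sentences and a software option, plus wider intervals. Under (b), a single-contrast interval with Mancl-DeRouen and t(9) is (2.262/1.960) x (10/9) = 1.28 times the default width. Patients, visits and data collection do not change.

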### **8.3 Subject Population(s) for Analysis**

The subject population for analyses will include all patients who receive the Botox injection. We intend to minimize loss to follow-up; however, if patients drop out of the study, we will attempt to use statistical methods that allow for missing outcomes (e.g. GEE/Linear models for repeated data) so that all available data can be used for analysis.

### **8.4 Planned Interim Analysis:**

No interim analyses are planned for this study.

## **9 Data Collection, Handling and Record Keeping**

### **9.1 Data Confidentiality**

- Subject encounters include questionnaires will be submitted to the electronic record on RedCap according to the subject's respective medical record number. Following conclusion of the study, the investigators will utilize the database to review the medication effect and perform data analysis.
- Except for publication, data will not be shared with other researchers and identifiable information will not be released to third parties.

#### **9.1.1 Confidentiality of Subject Records**

By signing the protocol, the Investigator agrees that IRB representative may consult and/or copy study documents in order to verify CRF data. By signing the consent form, the subject agrees to this process. If study documents will be photocopied during the process of verifying CRF information, the subject will be identified by unique code only and full names and similar identifying information (such as medical record number or social security number) will be masked.

The Clinical Site Investigators will ensure that the identity of subjects will be protected. All study records will be maintained in a secure fashion with access limited to essential study personnel only. All study documents submitted to the Coordinating Center will have identifiers removed other than dates of birth and service and subjects will be identified with a study-specific identification number only. The Clinical Site Investigators will maintain, in a secure location, an enrollment log that includes subject identifying information and links subjects to their study-specific identification number.

### **9.2 Data Capture**

#### **9.2.1 Source Documents**

1. Physical therapy clinic notes
2. Procedure note
3. Copies of transcription certified after verification as being accurate and complete from clinic visits with investigators
4. Completed UWRI questionnaires from both clinic and telephone encounters that had been entered into RedCap

### 9.2.2 Data Collection Tools

Study will utilize RedCap for data collection and management.

### 9.3 Data Management

Investigator, [name], will serve as the DCC for the study. The DCC agrees to be responsible for implementing and maintaining quality control and quality assurance systems with written standard operation procedures (SOPs) to ensure that trial is conducted and data are generated, documented, and reported in compliance with the protocol, accepted standards of Good Clinical Practice (International Conference on Harmonization E6), and all applicable federal, state, provincial, and local laws, rules, and regulations relating to the conduct of the clinical trial in an ongoing and auditable manner.”

### 9.4 Records Retention

Data will be retained for 4 years following the conclusion of the study.

## 10 Assessment of Safety

### 10.1 Specifications of Safety Parameters

Lower extremity weakness will be both quantitative and qualitative data.

Bruising, bleeding, pain, redness, or swelling where the injection was given will be qualitative data

#### 10.1.1 Definition of Adverse Events (AE)

Adverse event means any untoward medical occurrence associated with the use of an intervention in humans, whether or not considered intervention-related (21 CFR 312.32 (a)).

#### 10.1.2 Definition of Serious Adverse Events (SAE)

Serious adverse event or serious suspected adverse reaction. An AE or suspected adverse reaction is considered "serious" if, in the view of either the investigator or sponsor, it results in any of the following outcomes: death, a life-threatening adverse event, inpatient hospitalization or prolongation of existing hospitalization, a persistent or significant incapacity or substantial disruption of the ability to conduct normal life functions, or a congenital anomaly/birth defect. Important medical events that may not result in death, be life-threatening, or require hospitalization may be considered serious when, based upon appropriate medical judgment, they may jeopardize the patient or subject and may require medical or surgical intervention to prevent one of the outcomes listed in this definition.

